8 STATISTICAL METHODS

Statistical analyses will focus on estimation of overall response rates in patients with platinum-resistant ovarian cancer as stated in the Primary Objective. Specific definitions for complete response (CR), partial response (PR), stable disease (SD) or progressive disease (PD) are defined in the Primary Endpoint section according to physical exam findings, serum CA-125 levels and imaging studies. Response frequencies and percentages will be tabulated for all four groups and then an overall frequency of response (CR or PR) v. non-response (SD or PD) will be calculated along with a onesided lower limit 95% confidence interval, consistent with the approach used to specify staging of accrual. For the secondary objective, the Kaplan-Meier method will be utilized to estimate the median and overall distribution of progression-free survival. Toxicity will also be evaluated as a secondary objective and grades will be summarized by counts and frequencies. For description of other continuous variables, means, standard deviations, minimum and maximum values will be used. Other categorical variables will be summarized by counts and frequencies. In addition, the extent to which treatment is completed will be monitored and tabulated according to the number of complete weeks of treatment.

Total anticipated accrual to this phase II single-arm trial is 30 patients. Recruitment will be completed in two stages with 10 patients accrued in the first stage and 20 accrued in the second stage according to Simon's two-stage design (Simon, 1989; Jung et al. 2004) with a null hypothesis that the true response rate is less than or equal to 5% and 5% type I error and 80% power when the true response rate is greater than or equal to 20%. In the first stage, if there are 0 responses (CR or PR) in the 10 patients that are accrued, the study will be stopped. Otherwise, 20 additional patients will be accrued, with rejection of the null hypothesis occurring if 4 or more responses are observed in the total 30 patients. On 10/12/16 the Northwestern DSMC reviewed the first 9 evaluable patients and approved the study to open to an additional 21 patients. Calculations were conducted using the online software at

http://cancer.unc.edu/biostatistics/program/ivanova/SimonsTwoStageDesign.aspx.

With an expected response rate of 20%, if all 30 patients are accrued, a one-sided 95% lower-limit confidence interval will have a distance from the sample proportion to the lower limit of about 14%.

For *exploratory aims* we will proceed as follows. The first exploratory endpoint is the expression of proteins that play a role in VEGF signaling and other relevant oncogenic pathways. The level of expression of each protein will be correlated via ANOVA with response to treatment (CR, PR, SD, PD); The second exploratory endpoint is a retrospective genetic mutation burden to be correlated via ANOVA or contingency table analysis with response to treatment (CR, PR, SD, PD).

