3 PATIENT SELECTION

The target population for this study is patients with recurrent or persistent, platinum resistant epithelial ovarian, fallopian tube or primary peritoneal carcinoma. This will be a multicenter trial conducted at Northwestern Medicine. Northwestern University will serve as the lead site and coordinating center for this study. Participating sites will include Northwestern Medicine Cancer Center Warrenville and the Northwestern Medicine Cancer Center Delnor and Northwestern Lake Forest Hospital.

A total of 30 subjects will be needed for this trial. Approximately 6 potentially eligible patients are seen per month, and it is anticipated that at least 3 per month will be accrued (once all sites are up and running). Potential patients may be referred to the Principal Investigator (PI) at Northwestern University, [name], at [contact], or to the local PI at each participating site.

Eligibility will be evaluated by the study team according to the following criteria. Eligibility waivers are not permitted. Subjects must meet all of the inclusion and none of the exclusion criteria to be registered to the study. Study treatment may not begin until a subject is registered. Please refer to Section 10 for complete instructions regarding registration procedures.

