5.4.2 Evaluation of Non-Target Lesions

Complete Response (CR): Disappearance of all non-target lesions. All lymph nodes must be non-pathological in size (<10 mm short axis).

Note: If CA-125 is initially above the upper normal limit, it must normalize for a patient to be considered in complete clinical response.

Non-CR/Non-PD: Persistence of one or more non-target lesion(s)

Progressive Disease (PD): Appearance of one or more new lesions and/or unequivocal progression of existing non-target lesions. Unequivocal progression should not normally trump target lesion status. It must be representative of overall disease status change, not a single lesion increase.

Not evaluable (NE): When at least one non-target lesion is not evaluated at a particular time point.

Although a clear progression of only 'non-target' lesions is exceptional, the opinion of the treating physician should prevail in such circumstances, and the progression status should be confirmed at a later time by the review panel (or Principal Investigator).

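### Section 8 counts only SD and PD as non-response and does not name the response-rate denominator, so a treated but unassessed patient has no stated place

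*Combined protocol and SAP*

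**What the plan says.** Section 8 (Statistical Methods) sets up a table of CR, PR, SD and PD: "Response frequencies and percentages will be tabulated for all four groups". The primary result collapses this table into two classes: "an overall frequency of response (CR or PR) v. non-response (SD or PD) will be calculated". A one-sided 95% lower limit accompanies the rate. The section names no denominator or analysis population and has no row for a patient without an assessment.

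The design text in the same section counts accrued patients. For stage 1: "In the first stage, if there are 0 responses (CR or PR) in the 10 patients that are accrued, the study will be stopped". For the final decision: "with rejection of the null hypothesis occurring if 4 or more responses are observed in the total 30 patients". The precision statement applies "if all 30 patients are accrued, a one-sided 95% lower-limit confidence interval", and Section 3 says "A total of 30 subjects will be needed for this trial".

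The one count reported so far is on a different basis. The monitoring committee "reviewed the first 9 evaluable patients and approved the study to open to an additional 21 patients". Evaluable is not defined in the protocol. The only not-evaluable category is in Section 5.4.2, "When at least one non-target lesion is not evaluated at a particular time point". It describes non-target lesions at one visit and is not carried through to a patient's best response or to Section 8.

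**The concern.** SD and PD both need data: a target-lesion sum (5.4.1), non-target findings (5.4.2) or a CA-125 level (5.4.3). Death is an event for progression-free survival (5.6), but no response criterion makes it PD. A patient who starts tivozanib and dies, withdraws consent or is lost before any post-baseline assessment is therefore neither a responder nor a non-responder under Section 8.

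Such a patient contributes no response. Leaving the patient out shrinks the denominator and leaves the numerator alone, so the error has one direction: the estimate and its lower limit go up. Estimating the response rate is the stated focus of the analysis, and a single-arm trial has no control arm in which the same omission would show. If the denominator is not fixed before the final analysis, it could be chosen once outcomes are known.

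**Working it through.** **Inputs.** From Section 8: null rate 5%, alternative 20%, 5% type I error, 80% power, stages of 10 and 20, stop at 0 responses in stage 1, reject at 4 or more of 30, one-sided 95% lower limit. The documents give no number of unassessed patients, so m = 0, 1, 2, 3 of 30 is an assumption.

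**The plan's own figures.** The probability of rejecting is the sum over a = 1 to n1 of P(a responses in n1) × P(at least 4 − a responses in n2).
- 10 + 20: 0.0513 at a 5% rate and 0.814 at a 20% rate. This reproduces the stated power, with type I error just above the stated 5%.
- 9 + 21: 0.0489 and 0.793.

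The plan names no interval method, and its stated distance of about 14% at a 20% rate does not identify one. With 6 of 30, the exact one-sided distance is 20.0% − 9.09% = 10.9 points. The normal approximation gives 1.645 × √(0.2 × 0.8/30) = 12.0 points, and 14.3 points needs the multiplier 1.96. Limits are therefore shown by more than one method.

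**Effect of omission.**
- Response rate = x/(30 − m).
- Fixed-size exact limit = 5th percentile of Beta(x, n − x + 1), with n = 30 − m.
- Two-stage limit = the rate p at which P(at least 1 response in stage 1 and at least x in total) = 0.05. The unassessed are assumed to be in stage 2.

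For x = 4 responders:

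| Unassessed | Rate | Fixed-size limit | Two-stage, 10 + 20 | Two-stage, 9 + 21 |
|---|---|---|---|---|
| 0 | 4/30 = 13.3% | 4.69% | 4.96% | 5.04% |
| 1 | 4/29 = 13.8% | 4.85% | 5.11% | 5.19% |
| 2 | 4/28 = 14.3% | 5.03% | 5.27% | 5.35% |
| 3 | 4/27 = 14.8% | 5.22% | 5.45% | 5.52% |

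For x = 6 responders (the plan's 20%), the rate is 20.0%, 20.7%, 21.4%, 22.2% and the fixed-size limit 9.09%, 9.42%, 9.77%, 10.15%.

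Each omitted patient adds about 0.5 to 0.8 points to the rate and 0.15 to 0.4 points to the limit. With exactly 4 responders, the reported limit passes the 5% null at two omitted patients (fixed-size) or one (10 + 20). With 9 + 21 it is above 5% throughout. The 10 + 20 column follows the stated design. The 9 + 21 column treats the interim as a stop at 0 of 9, a rule the plan does not state.

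**Decision rule.** Four responses remain four whether or not an unassessed patient is in the denominator. If 30 patients are treated and none replaced, the rule gives the same answer either way.

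**The case against.** The strongest reply is that exclusion is inferred. A table with four rows can still report percentages of 30, and every denominator Section 8 does state is of accrued patients. The sentence on the lower limit also ties the interval to the approach used for staging accrual. That clause may refer only to the limit being one-sided, but it fits 30 better than a smaller number. Response is also assessed under RECIST 1.1 by reference (5.1), and these documents do not show whether that guideline settles the matter. What stands is that the accrual wording points to 30. What remains is that the section does not say so, its definition of non-response leaves the unassessed out, and its only reported count is of evaluable patients.

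A second reply is that few patients can be affected. Examination and CA-125 precede each cycle, CA-125 alone can give SD or PD (5.4.3), and imaging continues off treatment until progression (7.1, footnote 11). This is right and limits the size. It does not cover a patient who stops in cycle 1 and then dies, or who withdraws consent or is lost to follow-up, both of which Section 4.6 lists.

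A reader might infer from the interim sentence that a tenth patient was treated and then excluded or replaced. The documents do not support that. The 21 further patients make 30 when added to the 9 (9 + 21 = 30), but nothing says how many had been treated at the review, and no replacement rule is given.

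**Conclusion.** The point holds as an unstated denominator, with a definition of non-response that permits an upward-only error in the primary estimate. It does not hold as a finding that the plan excludes unassessed patients or that any were excluded.

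It is a minor to moderate point. With 4 responders and up to three unassessed patients (an assumed number), the rate rises from 13.3% to at most 14.8% and the fixed-size exact limit from 4.69% to at most 5.22%. Only in this borderline case can the choice of denominator move the limit across 5%.

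A reader might also infer that the trial's decision is at risk. It is not, provided 30 patients are treated without replacement. If more than 9 had been treated at the interim and counting went on from the 9, more than 30 would be treated in all, and the plan would not say which 30 the rule uses. The documents do not show which case applies.

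**What to change.** In Section 8, before the final analysis:
- State that the primary response rate and its lower limit use all patients who started tivozanib.
- Add a row for not evaluable or not assessed, counted as non-response in the denominator.
- Define evaluable, and give the evaluable-only rate only as a sensitivity analysis.
- State whether the 30 for the decision rule are the first 30 treated, including any who had been treated but were not among the 9 at the interim review.

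The cost is a few sentences and one table row, with no added patients. The reported rate and limit may be slightly lower than on an evaluable-only basis. The wording does not change the power of the count rule: any loss of power comes from patients going unassessed, which happens under the current text as well.

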9 ADVERSE EVENTS

This study will be conducted in compliance with the Data Safety Monitoring Plan (DSMP) of the Robert H. Lurie Comprehensive Cancer Center of Northwestern University (please refer to Appendices for additional information). The level of risk attributed to this study requires high-risk monitoring as outlined in the DSMP. In addition, the study will abide by all safety reporting regulations, as set forth in the Code of Federal Regulations.

9.1 Adverse Event Monitoring

Adverse event data collection and reporting, which are required as part of every clinical trial, are done to ensure the safety of subjects enrolled in the studies as well as those who will enroll in future studies using similar agents. Adverse events are reported in a routine manner at scheduled times during a trial (see Section 7 for timepoints). In addition, certain adverse events must be reported in an expedited manner to allow for optimal monitoring and patient safety and care.

All patients experiencing an adverse event, regardless of its relationship to study drug, will be followed until:

- the adverse event resolves or the symptoms or signs that constitute the adverse event return to baseline;
- any abnormal laboratory values have returned to baseline;
- there is a satisfactory explanation other than the study drug for the changes observed; or
- death.

9.2 Definitions & Descriptions

9.2.1 Adverse Event

An adverse event (AE) is any untoward medical occurrence in a patient receiving study treatment and which does not necessarily have a causal relationship with this treatment. An AE can therefore be any unfavorable and unintended sign (including an abnormal laboratory finding), symptom, or disease temporally associated with the use of an experimental intervention, whether or not related to the intervention.

Recording of AEs should be done in a concise manner using standard, acceptable medical terms. In general, AEs are not procedures or measurements, but should reflect the reason for the procedure or the diagnosis based on the abnormal measurement. Preexisting conditions that worsen in severity or frequency during the study should also be recorded (a preexisting condition that does not worsen is not an AE). Further, a procedure or surgery is not an AE; rather, the event leading to the procedure or surgery is considered an AE.

If a specific medical diagnosis has been made, that diagnosis or syndrome should be recorded as the AE whenever possible. However, a complete description of the signs, symptoms and investigations which led to the diagnosis should be provided. For example, if clinically significant elevations of liver function tests

are known to be secondary to hepatitis, "hepatitis" and not "elevated liver function tests" should be recorded. If the cause is not known, the abnormal test or finding should be recorded as an AE, using appropriate medical terminology (e/g/ thrombocytopenia, peripheral edema, QT prolongation).

9.2.2 Severity of AEs

Note, some hematology studies may choose to grade toxicity using alternatives to the CTCAE v4.03 (e.g., iwCLL criteria). When an alternative is used, please modify this section as needed. If using the CTCAE state:

All non-hematologic adverse events will be graded according to the NCI Common Terminology Criteria for Adverse Events (CTCAE) version 4.03. The CTCAE v4.03 is available at http://ctep.cancer.gov/reporting/ctc.html.

If no CTCAE grading is available, the severity of an AE is graded as follows:

- Mild (grade 1): the event causes discomfort without disruption of normal daily activities.
- Moderate (grade 2): the event causes discomfort that affects normal daily activities.
- Severe (grade 3): the event makes the patient unable to perform normal daily activities or significantly affects his/her clinical status.
- Life-threatening (grade 4): the patient was at risk of death at the time of the event.
- Fatal (grade 5): the event caused death.
- 9.2.3 Serious Adverse Events (SAEs)

All SAEs, regardless of attribution, occurring from time of signed informed consent, through 30 days after the last administration of study drug, must be reported upon discovery or occurrence.

An SAE is defined in regulatory terminology as any untoward medical occurrence that:

• Results in *death*.

If death results from (progression of) the disease, the disease should be reported as event (SAE) itself.

• Is life-threatening.

The patient was at risk of death at the time of the event; it does not refer to an event that hypothetically might have caused death if it were more severe.

• Requires in-patient hospitalization or prolongation of existing hospitalization for ≥ 24 hours.

- Results in persistent or significant disability or incapacity.
- Is a congenital anomaly/birth defect.
- Is an important medical event.

Any event that does not meet the above criteria, but that in the judgment of the investigator jeopardizes the patient, may be considered for reporting as a serious adverse event. The event may require medical or surgical intervention to prevent one of the outcomes listed in the definition of "Serious Adverse Event".

For example: allergic bronchospasm requiring intensive treatment in an emergency room or at home; convulsions that may not result in hospitalization; development of drug abuse or drug dependency.

9.2.4 Unanticipated Problems Involving Risks to Subject or Others

A UPIRSO is a type of SAE that includes events that meet ALL of the following criteria:

- Is *unanticipated* in terms of nature, severity, or frequency
- Places the research subject or others at a different or greater risk of harm
- Is deemed to be *at least possibly related* to participation in the study.

9.3 Adverse Event Reporting

9.3.1 Routine Reporting

All routine adverse events, such as those that are expected, or are unlikely or definitely not related to study participation, are to be reported on the appropriate eCRF. Routine AEs will be reviewed by the Data and Safety Monitoring Committee (DSMC) according to the study's phase and risk level, as outlined in the DSMP.

9.3.2 Determining if Expedited Reporting is Required

This includes all events that occur within 30 days of the last dose of protocol treatment. Any event that occurs more than 30 days after the last dose of treatment and is attributed (possibly, probably, or definitely) to the agent(s) must also be reported accordingly.

- 1) Identify the type of adverse event using the NCI CTCAE v 4.03.
- 2) Grade the adverse event using the NCI CTCAE v 4.03.
- 3) Determine whether the adverse event is related to the protocol therapy. Attribution categories are as follows:

Definite: AE is clearly related to the study treatment. Probable: AE is likely related to the study treatment. Possible: AE may be related to the study treatment. Unlikely: AE not likely to be related to the study treatment. Unrelated: AE is clearly NOT related to the study treatment.

4) Determine the prior experience of the adverse event.

Expected events are those that have been previously identified as resulting from administration of the agent. An adverse event is considered unexpected, for

expedited reporting purposes only, when either the type of event or the severity of the event is not listed in:

- the current protocol
- the drug package insert
- the current Investigator's Brochure

9.3.3 Expedited Reporting of SAEs/Other Events

9.3.3.1 Reporting to the Northwestern University QAM/DSMC

All SAEs must be reported to the assigned QAM within 24 hours of becoming aware of the event. Completion of the NU CRO SAE Form, provided as a separate document, is required.

The completed form should assess whether or not the event qualifies as a UPIRSO. The report should also include:

- Protocol description and number(s)
- The patient's identification number
- A description of the event, severity, treatment, and outcome (if known)
- Supportive laboratory results and diagnostics
- The hospital discharge summary (if available/applicable)

All SAEs will be reported to, and reviewed by, the DSMC at their next meeting.

9.3.3.2 Reporting to the Northwestern University IRB

The following information pertains to the responsibilities of the lead site (Northwestern University). Additional participating sites should follow their local IRB guidelines for reporting to their local IRBs.

- Any death of an NU subject that is unanticipated in nature and at least possibly related to study participation will be promptly reported to the NU IRB within 24 hours of notification.
- Any death of an NU subject that is actively on study treatment (regardless of whether or not the event is possibly related to study treatment)
- Any death of a non-NU subject that is unanticipated and at least possibly related and any other UPIRSOs will be reported to the NU IRB within 5 working days of notification.
- All other deaths of NU subjects not previously reported, other non-NU subject deaths that were unanticipated and unrelated, and any other SAEs that were not previously reported as UPIRSOs will be reported to the NU IRB at the time of annual continuing review.
- 9.3.3.3Reporting to the FDA (to be done by QAM if applicable) The FDA will be notified within 7 calendar days of any SAE that is associated with study treatment, is unexpected, and is fatal or life-threatening.

The FDA will be notified within 15 calendar days of any SAE that is associated with the study treatment, unexpected, and serious but *not fatal or life*-

threatening. This includes any previous SAEs that were not initially deemed reportable, but are later determined to meet the criteria for reporting (i.e. by the DSMC).

All other SAEs will be reported on an annual basis as part of the annual FDA report.

9.3.3.4 Reporting to AVEO Pharmacovigilance/Drug Safety and NCCN AVEO Pharmacovigilance/Drug Safety and NCCN must be informed of ALL SAE/suspected unexpected serious adverse reaction (SUSAR) reports within 24 hours of first awareness.

The Sponsor-Investigator must comply with any applicable requirements related to the reporting of SAEs involving his/her subjects to the IRB that approved the study.

All SAEs should be recorded on the CRO SAE Form and sent to AVEO and NCCN:

 AVEO SAE reports should be sent to Parexel GPPG at [contact]. If submission via email is not possible or delayed then submission via fax (NA: [contact]) is acceptable.

9.3.4 Safety Reporting Requirements for IND Holders

For Investigator Sponsored IND Studies there are some additional reporting requirements for the FDA in accordance with the guidance set forth in 21 CFR 312.32. Sponsor-investigators of studies conducted under an IND must comply with the following safety reporting requirements:

